	
mg/day). Then maintenance dosing of 800 mg BID (1600 mg/day) from Day 2 (beginning 18-24 hours after the loading dose on Day 1).
 
 • Patients with Child-Pugh liver impairment of grade A will have their maintenance dose decreased to 600 mg BID • The total duration of treatment is expected to be 10 days.

Duration of Study Participation
	
The total anticipated duration of the study for each patient is up to 28 days.

Statistical Methods
	
To address our primary objective, time until viral shedding cessation will be compared between the two treatment arms using a two-sided Wald test derived from a Cox proportional hazards model adjusted for age and sex and stratified by site. The test will be performed at the two-sided $\alpha = 0.05$ level of significance. The hazard ratio for shedding cessation will be estimated, along with its 95% confidence interval, from a Cox proportional hazards model. If the proportional hazards assumption is not met, we will consider an extended Cox model that relaxes the proportional hazards assumption. The log rank test will also be performed.
 
The distribution of viral shedding cessation will be estimated using the Kaplan-Meier method, and Kaplan-Meier curves will be presented for each treatment arm. Time to shedding cessation along with 95% confidence intervals will be presented for each treatment arm.
 
The rate of hospitalizations and ED visits will be estimated along with 95% confidence intervals by each arm. In addition, we will compare between arms the time to each of respiratory failure, hospitalization or deaths and the corresponding composite of all such events using Kaplan-Meier methods. The frequency of adverse events and serious adverse events will be tabulated by type and by treatment arm. AEs will be compared by arm using the Chi-squared test or Fisher’s exact test, as appropriate, in the safety analysis set.
 
An interim analysis for safety and overwhelming efficacy will be performed once 50% of patients have 24 hours of follow-up complete. Enrollment will pause once 50% of patients have received treatment and will remain paused until the DSMC makes their recommendation after their safety review.

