7.1 Day 1 (PRE-DOSE)

- Obtain informed consent.
- Verify eligibility per the inclusion and exclusion criteria. (See Sections 5.1 and 5.2)
 - Review and record medical history, including tobacco use, to ensure there are no exclusionary illnesses.
 - Review and record concomitant medications for possible prohibited medications. (See Section 6.7)
- If subject is female of child-bearing potential and meets inclusion criteria 11.c, obtain urine pregnancy test and proceed if result is negative.
- Measure and record vital signs (BP, HR, Temp, Resp).
- Collect and record SPO2 by Finger Sensor
- Perform Physical exam (may be done by the Principal Investigator or their designee)
- Complete baseline symptom survey to establish severity of symptoms (if present)
- Collect oropharyngeal swab for virologic testing (RT-PCR) and resistance analysis.
- Collect two nasal swabs for antigen testing and molecular viability testing.
- Collect blood samples for
 - Uric acid
 - CRP
 - Hematology and clinical chemistry laboratory analyses (samples collected within 48 hours of enrollment are acceptable):
 - Resistance analysis
 - Optional: Antibodies to SARS-CoV-2.
 - Optional: Biobanking
 - Optional: Pre-dose PK

- Perform subject randomization (via EDC) to establish treatment arm (favipiravir + SOC or placebo + SOC).
- Explain in home procedures for the study (self-sampling of nasal swabs, temperature, SPO2, completing the daily questionnaire and the optional collection of stool sample).
- Provide supplies to research subject and review the calendar of return visits.
- Optional: Explain that stool sample from first bowel movement after enrollment should be collected in Zymo fecal tube and brought back to Day 5 follow-up visit. If the first bowel movement sample cannot be collected, it is permitted to collect a subsequent bowel movement sample.

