9.1 General Considerations

For the primary comparison, the following will be tested:

- Null hypothesis: time to cessation of oral shedding is equal in control and treatment;
- Alternative hypothesis: time to cessation of oral shedding differs between control and treatment.

Hypothesis tests will be two sided and conducted at an overall $\alpha = 0.05$ level of significance.

The number of hospitalizations and emergency department visits will be estimated for each arm, with 95% confidence intervals. The frequency of adverse events and serious adverse events will be

tabulated by type and by treatment arm. AEs will be compared by arm using the Chi-squared test or Fisher's exact test, as appropriate, in the safety analysis set.

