9.5 Stratification, Subgroup Analysis and Pooled Analysis

Following consent, those subjects meeting all entry criteria will be randomized in a 1:1 ratio

Treatment Arm: favipiravir + SOC

Control Arm: placebo + SOC

Randomization will be stratified by age (≥ 50 and < 50 years old) and sex.

Members of the same household may participate in the study as long as the inclusion and exclusion criteria are met. Because this is a double-blind, placebo-controlled trial, subjects from the same household will be randomized just as any other subject.

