9.6 Efficacy Endpoint Analysis

Descriptive analyses

Descriptive statistics (proportions for categorical variables, means, medians, standard deviations, and interquartile ranges for continuous variables) will be reported for all key patient variables, including baseline and demographic characteristics, use of medications, compliance, and study completion status. Data that are missing on key patient characteristics and the outcome will be fully described, including any patterns of missingness (i.e., any relationships between missingness of a variable and patient characteristics).

A CONSORT diagram displaying the number of patients screened, eligible, and consented along with reasons for ineligibility will be provided. Graphical tools such as histograms, boxplots, and scatterplots will be created to assess quality of data and to display patterns over time.

Primary efficacy analysis

Time until shedding cessation will be compared between the two treatment arms using a Cox proportional hazards model adjusted for age and sex and stratified by site. The test will be performed at the $\alpha = 0.05$ level of significance. The hazard ratio for shedding cessation will be estimated, along with its 95% confidence interval, from a Cox proportional hazards model. If the proportional hazards assumption is not met, we will consider an extended Cox model that relaxes the proportional hazards assumption.

The distribution of shedding cessation will be estimated using the Kaplan-Meier method, and Kaplan-Meier curves will be presented for each treatment arm. Time to shedding cessation at the end of the study period along with 95% confidence intervals will be presented for each treatment arm.

Secondary efficacy analyses

The distribution of cessation of symptoms will be estimated using the Kaplan-Meier method, and Kaplan-Meier curves will be presented for each treatment arm. Time to cessation of symptoms at the end of the study period along with 95% confidence intervals will be presented for each treatment arm. The hazard ratio for cessation of symptoms will be estimated, along with its 95% confidence intervals, from a Cox proportional hazards model. Time to cessation of symptoms will be determined by analysis of daily questionnaires. Resolution of symptoms requires that symptoms are mild or absent for at least 24 hours.

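### The symptom-cessation Cox model names no covariates or strata; read literally it is valid, but it gives up power if age, sex or baseline symptom severity is prognostic

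*Combined protocol and SAP*

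**What the plan says.** Section 9.6 compares time to shedding cessation between arms "using a Cox proportional hazards model adjusted for age and sex and stratified by site". Its paragraph on symptom cessation has no matching sentence. It plans Kaplan-Meier curves and then states: "The hazard ratio for cessation of symptoms will be estimated, along with its 95% confidence intervals, from a Cox proportional hazards model". It sets no test, alpha or power target for this endpoint.

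On design, Section 9.5 says "Randomization will be stratified by age" (50 and over against under 50) and sex. Section 7.1 has a baseline symptom severity survey completed before the first dose, but no analysis model in the protocol uses it. The multiple imputation paragraph in 9.6 puts baseline characteristics into the imputation model, which does not put them into the analysis model.

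The event itself is defined in two ways. The synopsis (secondary endpoint 5) requires symptoms to be absent for at least 24 hours. Section 9.6 also accepts symptoms that are mild.

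The opening of Section 9 defers full analysis details to a formal SAP, to be completed after study initiation. The documents supplied contain no fuller specification of this model.

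**The concern.** Symptom duration is part of the first secondary objective. Entry needs only one symptom from a long list, and the synopsis describes the population as asymptomatic or with mild to moderate symptoms, so participants start from very different points. Day 1 severity is then a natural predictor of when symptoms stop. Under the 9.6 definition the link is direct: someone whose symptoms are all mild on Day 1 could meet the event almost at once, while someone with moderate symptoms could not.

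Leaving a strong predictor out of a Cox model moves the treatment hazard ratio towards 1 and lowers power. Leaving out factors used to stratify the randomisation tends to make the model-based interval somewhat too wide. Both costs would be avoidable, because the data are collected before dosing. There is also a pre-specification issue. Section 9.2 describes a sample-size re-estimation recommended by the DSMB, so this text postdates the start of enrolment, and the covariates for this endpoint are still open.

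**Working it through.** **The plan's own figures.** There is none to reproduce for this endpoint. The events, power, hazard ratio and medians in Section 9.2 all concern shedding.

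**Inputs from the documents.** 180 randomised (9.2), 1:1 (9.5), balanced within age group and sex (9.5), 28 days of follow-up (3.1), and tests at two-sided 0.05 (9.1: "Hypothesis tests will be two sided"). The 10% dropout that 9.2 gives for the control arm was applied to both arms.

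**Inputs assumed.** Conditional treatment hazard ratio 1.5, exponential times, control median 10 days, 40% in one age group, half of each sex, and a standardised severity score. Prognostic hazard ratios are shown in the table. N = 180 treats every randomised participant as having symptoms to resolve. The number who will is not stated, so N = 120 was also run.

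**Method.** 1,500 simulated trials per row, with a Wald test from three Cox models: treatment only; plus age and sex; plus age, sex and severity. Monte Carlo error on power is at most √(0.5 × 0.5 / 1500) = 1.3 points. Site strata were not simulated.

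Results at N = 180 (estimated hazard ratio, power):

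| Prognostic HR: age / sex / severity per SD | Treatment only | + age, sex | + age, sex, severity |
|---|---|---|---|
| 1 / 1 / 1 | 1.50, 70.9% | 1.51, 71.7% | 1.51, 71.8% |
| 0.8 / 1.1 / 1 | 1.50, 70.7% | 1.51, 72.3% | 1.51, 72.2% |
| 0.67 / 1.25 / 1 | 1.49, 68.8% | 1.52, 72.9% | 1.52, 72.3% |
| 0.5 / 1.5 / 1 | 1.45, 62.1% | 1.51, 71.3% | 1.52, 70.5% |
| 0.8 / 1.1 / 0.8 | 1.49, 70.0% | 1.50, 71.1% | 1.52, 72.9% |
| 0.67 / 1.25 / 0.67 | 1.43, 59.1% | 1.45, 61.2% | 1.51, 70.4% |
| 0.67 / 1.25 / 0.5 | 1.37, 47.5% | 1.38, 49.2% | 1.51, 66.7% |

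**Gains.**
- Age and sex alone: 72.3 − 70.7 = 1.6; 72.9 − 68.8 = 4.1; 71.3 − 62.1 = 9.2 points.
- Full model when severity matters: 72.9 − 70.0 = 2.9; 70.4 − 59.1 = 11.3; 66.7 − 47.5 = 19.2 points.
- Nothing prognostic: 71.8 − 70.9 = 0.9 points, within simulation error.
- At N = 120 the corresponding full-model gains are 53.7 − 51.1 = 2.6, 52.9 − 42.8 = 10.1 and 54.2 − 35.2 = 19.0 points.

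**Check by formula.** Schoenfeld power is Φ(½√d · ln HR − 1.96). The moderate severity row averaged d = 152.8 events with a treatment-only estimate of 1.43: 6.181 × 0.3577 − 1.96 = 0.251, and Φ(0.251) = 59.9%, against 59.1% simulated. In the strong row (d = 148.2, 1.366): 6.087 × 0.3119 − 1.96 = −0.062, giving 47.5%, as simulated. The loss is therefore explained by the smaller log hazard ratio.

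**Validity.** With no treatment effect, the treatment-only hazard ratio stays between 0.99 and 1.00 at N = 180 and rejection is 3.4% to 5.3% (Monte Carlo error about 0.6 points). The low end comes from strongly prognostic age and sex. At N = 120 it is 3.6% to 6.1%, and the full model gives 4.9% to 6.7%, so the N = 120 gains may be slightly flattered.

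**Second set of assumptions.** With 75 symptomatic participants per arm, hazard ratio 1.6, median 12 days and daily tied times, power rises from 66.9% to 71.9% when the severity log-hazard is 0.3 per SD, from 58.2% to 67.9% at 0.5, and from 49.1% to 68.1% at 0.7. The gains are 5.0, 9.7 and 19.0 points.

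**The case against.** The strongest reply is that silence is not a decision. The primary endpoint has an almost identical sentence, "The hazard ratio for shedding cessation will be estimated, along with its 95% confidence interval, from a Cox proportional hazards model", which also names no covariates, and details are deferred to a SAP. That stands in part: a reader might infer that the sponsor chose an unadjusted model, and the documents do not say so. But the primary sentence follows one that does name covariates, and the symptom sentence has nothing to inherit from.

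Second, a reader might infer that the treatment-only hazard ratio is biased. It is not. The shift towards 1 is non-collapsibility: the unadjusted model targets a marginal hazard ratio, the adjusted one a conditional hazard ratio, and both are legitimate.

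Third, no power is stated for this endpoint, so no promised power is eroded, and the larger losses depend on assumed prognostic strengths. That stands.

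Fourth, the synopsis sentence "The log rank test will also be performed" might be taken as an unstratified test of symptoms. It closes the paragraph on shedding, so it belongs to the primary endpoint, and nothing says whether it is stratified.

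Fifth, severity is not in the primary model either, so asking for it goes beyond the plan's own pattern, and no survey score is defined (Appendix A only points to the survey). Both facts are right. They mean that a score has to be defined, and that copying the primary covariates would not be enough: in the moderate row age and sex alone reach 61.2%, against 70.4% with severity.

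**Conclusion.** The concern holds as an efficiency and specification point. Section 9.6 leaves the symptom-cessation model without covariates or strata, although it specifies them for the primary model and the data exist. Followed as written, the analysis is valid, and sometimes slightly conservative, but likely to be less powerful than it could be.

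At N = 180 with a conditional hazard ratio of 1.5, the loss is about 2 to 9 points of power for age and sex alone, about 3 to 19 points if baseline severity is also prognostic, and about 0 if none of them is. These figures illustrate the range and do not forecast this trial. They rest on assumed prognostic effects, an assumed 10-day median, and all randomised participants contributing; the median also depends on which definition of cessation applies.

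The documents do not support saying that the sponsor chose to omit covariates, that the estimate is biased, that the test is invalid, or that power is certain to be lost.

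**What to change.** In Section 9.6, and in the SAP before unblinding:

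- Fit the symptom-cessation Cox model with treatment, age, sex and a Day 1 symptom-severity score, stratified by site as for the primary model.
- Define the score in advance from the baseline survey, for example the sum of item severities or the count of symptoms present.
- State that the reported hazard ratio is conditional on these covariates.
- Give one definition of symptom cessation in both the synopsis and 9.6, and say how participants who already meet it on Day 1, or who have no symptoms, are handled.
- Separately, stratify the supportive log-rank test for shedding in the synopsis by the age-by-sex randomisation strata.

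The cost is a few sentences and no new data collection. The downsides are small: a score must be defined, and the hazard ratio becomes conditional and so is not directly comparable with an unadjusted one.

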	
 2. Clinical worsening of COVID-19 in symptomatic subjects (clinical worsening defined the development of respiratory distress or symptoms that require hospitalization) or development of COVID-19 symptoms in asymptomatic subjects 3. Adverse events AEs and clinical laboratory tests for systemic safety including hematology and clinical chemistry 4. Development of antibodies to SARS-CoV-2 5. Time until cessation of symptoms (cessation of symptoms defined as absence of symptoms for at least 24 hours for those with mild symptoms). 6. Absence of development of any symptoms among those enrolled with asymptomatic infection. 7. Population PK analysis of favipiravir with assessment of maximum plasma concentration (C_{max}) and minimum plasma concentration (C_{min}) on Days 1, 5 and 10
Study Sites	Stanford University School of Medicine
Planned Enrollment	180 (90 in the favipiravir + SOC group and 90 in the placebo + SOC group)
Study Population	Adults with confirmed SARS-CoV-2 who are asymptomatic or experiencing mild to moderate symptoms
Subject Entry Criteria	
Inclusion Criteria (all questions must be answered YES)
 
 1. Adults (18-80) 2. Diagnosis of COVID-19 disease: 
 a. If symptomatic, but without signs of respiratory distress (as defined by SpO2 \leq94% on room air, RR \geq24, HR \geq110), with FDA-cleared molecular diagnostic assay positive for SARS-CoV-2 within 72 hours from initial swab to the time of commencing informed consent: Mild disease is defined as having at least 1 of the following: 
 i. Fever ($>98.7F$) b. Cough/Shortness of breath/dyspnea c. Fatigue d. Headache/Body aches e. Joint pain f. Chest pressure g. GI symptoms including nausea, vomiting, and/or diarrhea h. Abdominal pain i. Sore throat j. Nasal congestion k. Chills l. Runny nose

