
Individual Stopping Rule
	
A subject should be removed from favipiravir treatment if one of the following criteria is met:
 
 • AST or ALT > 8 x ULN • ALT or AST > 3 x ULN AND total bilirubin > 2X ULN • AST or ALT > 3 x ULN AND patient has right upper quadrant pain or eosinophilia

	
 • Uric acid >20mg/dL 
A subject whose treatment is terminated should remain in the study for appropriate follow up assessments.

Study Measurements: Efficacy, Safety and PK
	
Primary Measurement (Efficacy):
 
 1. Time to first of two negative tests based on nasal swab for RT-PCR taken daily from Day 1 to Day 10, and Days 14, 21, and 28. 
Secondary Measurements (Safety, Efficacy and PK):
 
 2. Oropharyngeal swab for nucleic acid (RT-PCR) taken Day 1, 5, 10, and 28. 3. Symptom improvement or worsening: Subjects will fill in a diary daily, recording the following symptoms: 
 a. Cough b. Sore throat c. Headache d. Nasal congestion e. Body aches and pains f. Fatigue g. Oral temperature taken after 4 pm and at least four hours after ingesting the most recent antipyretic (acetaminophen or NSAID) h. Dyspnea i. Shaking chills j. New loss of taste or smell k. GI symptoms including nausea, vomiting, and/or diarrhea l. Chest pain 4. Safety as assessed by: 
 a. Observed and reported adverse events b. Clinical laboratory evaluations of blood on Days 1, 5, 10, and 28 c. Physical Examination at screening (pre-dose Day 1), Days 10, and 28 d. Daily vital signs: pulse oximetry, heart rate, and temperature. 5. Optional Blood for determination of antibodies to SARS-CoV-2 will be obtained on Days 1 and 28. Collection of blood for antibodies is optional for sites. 6. Optional Blood for PK obtained pre-dose (within 30 minutes prior to dosing) and post-dose (45 to 75 minutes following dosing) on Days 1, 5 and 10. Collection of PK is optional for sites. 7. Optional Stool samples for determination of viral load in stool and microbiome characterization will be obtained in the following

	windows Day 1±5, 14±7, and 28±7. Collection of stool is optional for sites.
--	---

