5 SUBJECT POPULATION

5.1 Inclusion Criteria

The following criteria must be confirmed as “YES” except optional PK, antibody, and stool sample collection:

1. Adults (18 to 80 years old inclusive)
2. Diagnosis of COVID-19 disease:
 - a. If symptomatic without signs of respiratory distress (as defined by SpO₂ \geq 94% on room air, RR \leq 20, HR \leq 100), with FDA-cleared molecular diagnostic assay positive for SARS-CoV-2 within 72 hours from swab to the time of commencing informed consent. Mild disease is defined as having at least 1 of the following:
 - i. Fever ($>98.7^{\circ}\text{F}$)
 - b. Cough/Shortness of breath/dyspnea
 - c. Fatigue
 - d. Headache/Body aches
 - e. Joint pain
 - f. Chest pressure
 - g. GI symptoms including nausea, vomiting, and/or diarrhea
 - h. Abdominal pain
 - i. Sore throat
 - j. Nasal congestion
 - k. Chills
 - l. Runny nose
 - m. New loss of taste or smell
 - n. Abdominal pain
 - o. Rash
 - p. If asymptomatic, initial diagnosis obtained no more than 72 hours from initial swab to the time of commencing informed consent
3. Subject or their legal representative understands the requirements of the study and provides written informed consent prior to undergoing any treatment-related procedures.
4. Subject agrees to take daily nasal swabs (anterior nares) for Day 1 to Day 10 and Day 14, 21, and 28 using the study provided materials, and mail via FEDEX each sample on the day collected.
5. Subject agrees to record daily symptoms, temperature, oxygen saturation, and pulse using the study provided materials.
6. Subject agrees to obtain stool samples after the Day 1 visit, and 1-3 days before the Day 14 and Day 28 timepoints and agrees to bring the sample back in the provided stool collection kit to their subsequent appointment and to optionally mail in 4-month sample. Collection of stool is optional for sites.
7. Subject agrees to return to the study site for follow-up visits on Day 5, 10, and 28. The study site will be staffed by trained healthcare providers wearing full personal protective equipment and study site equipment will be disinfected between patients according to the same protocols

as a clinical setting. Subjects will be wearing masks, will be appropriately spaced, and the number of subjects assessed at each time will be limited.

8. Subject agrees to maintain home or other quarantine as recommended by the study physician, except to visit the study site as required by the protocol.

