9.4 Analysis Populations

The following analysis populations will be defined for the study:

The intent-to-treat (ITT) population will include all randomized patients. Patients will be analyzed according to their assigned treatment arm. All efficacy analyses will be completed in the ITT population.

The safety population will include all patients who receive study treatment. Patients will be analyzed according to actual treatment received. All safety analyses will be completed in the safety population.

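### Time to cessation of symptoms has two conflicting definitions, absence in secondary endpoint 5 and mild or absent in Section 9.6, and no named analysis set

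*Combined protocol and SAP*

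**What the plan says.** - **Synopsis, secondary endpoint 5** gives the event as "cessation of symptoms defined as absence of symptoms for at least 24 hours for those with mild symptoms".
- **Synopsis, secondary endpoint 6** handles the other patients separately: "Absence of development of any symptoms among those enrolled with asymptomatic infection".
- **Section 9.6, secondary efficacy analyses**, plans Kaplan-Meier curves and a Cox hazard ratio for cessation of symptoms, taken from the daily questionnaires. It then sets the event rule: "Resolution of symptoms requires that symptoms are mild or absent for at least 24 hours".
- **Section 9.4** states: "All efficacy analyses will be completed in the ITT population". That population is all randomised patients, and no exception is given.
- **Population.** The synopsis describes "Adults with confirmed SARS-CoV-2 who are asymptomatic or experiencing mild to moderate symptoms". Section 3.1 says asymptomatic or mild. Section 5.1 says "Mild disease is defined as having at least 1 of the following", followed by a symptom list without severity grades.
- **Measurement.** Section 7.1 has a baseline symptom survey to establish severity. Appendix A refers to that survey but does not reproduce it. The synopsis and Section 8.1 each list the diary symptoms, and the two lists differ.
- **Section 9** defers complete statistical detail to a formal SAP. The document contains no SAP text on this point.

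**The concern.** A patient whose mild symptoms persist has the event under Section 9.6 and does not have it under endpoint 5. The same diaries therefore give different event times, and the protocol supports both. If the choice is left until after unblinding, it can be influenced by the results.

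The trial's population makes the difference more than a matter of wording. A mild-or-absent rule suits patients who start worse than mild. A patient who starts with only mild symptoms satisfies its severity condition before the first dose, so the recorded time says nothing about recovery.

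Reducing the duration of symptoms is part of the first secondary objective, and this analysis supplies its curves and hazard ratio. The set of patients analysed is also open: endpoints 5 and 6 point to separate analyses of symptomatic and asymptomatic patients, but neither 9.4 nor 9.6 says so.

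**Working it through.** The plan states no event count, power or expected effect for this endpoint, so there is no figure to reproduce. The check is a comparison of the texts, followed by an illustration on assumed inputs.

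**1. Do both sentences define the same event?** Yes. The 9.6 sentence uses the word resolution, but it directly follows the sentence saying how time to cessation is determined, and no separate resolution endpoint exists.

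**2. Outcome by baseline state:**

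| Baseline state | Endpoint 5 (absence) | Section 9.6 (mild or absent) |
|---|---|---|
| All symptoms mild | event when all are gone for 24 h | severity condition met at entry; event at about the first diary unless the patient worsens within 24 h |
| At least one symptom worse than mild | rule not explicit (worded for mild symptoms) | event when all are mild or gone for 24 h |
| No symptoms | not covered; endpoint 6 applies | no rule stated |

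**3. How many patients are in the first row?** Unknown. Entry as mild disease requires only one listed symptom and is not a grade per symptom. The survey that would give the grades is not included.

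**4. Which symptoms must be absent?** Runny nose and rash are entry symptoms in 5.1 and diary items in 8.1, but they are not in the synopsis diary. A patient enrolled with only one of these would record no symptom on the synopsis list. Joint pain and abdominal pain are not separate items there either, though its items for body aches and pains and for GI symptoms may capture them. Both diary lists record oral temperature without saying what value counts as no fever. The only value in the documents is the entry criterion, above 98.7F.

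**5. Illustration.** From the plan: 180 patients, 1:1, 28 days. Assumed:
- 10% are asymptomatic and left out: 0.10 × 180 = 18, leaving 162.
- 15% or 40% of 180 are all-mild and do not worsen within 24 hours: 27 or 72 patients. As a share m of the 162, this is 27/162 = 16.7% or 72/162 = 44.4%.
- Symptom duration is exponential, rounded up to whole days and censored at day 28. The control median is 10 days and the hazard ratio is 1.5 under the absence rule.
- Patients worse than mild have the same event time under both rules.

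Results from simulated trials (1,000 per setting), with an unadjusted Cox model and Efron ties:

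| All-mild patients | HR, absence rule | HR, 9.6 rule |
|---|---|---|
| 27 of 162 | 1.51 | 1.40 |
| 72 of 162 | 1.50 | 1.24 |

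A typical 95% confidence interval under the absence rule is about 1.08 to 2.09.

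The medians follow directly. With share m recorded as events at the start, the curve is (1 − m) × 2^(−t/M), which reaches one half at t = M × log2[2(1 − m)]. Here M is 10 days for control and 10/1.5 = 6.7 days for favipiravir. Before rounding to whole days:
- m = 16.7%: log2(1.667) = 0.737, giving 7.4 and 4.9 days.
- m = 44.4%: log2(1.111) = 0.152, giving 1.5 and 1.0 days.

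**6. Sensitivity.** If all-mild patients recover faster (control median 6 days, against 12 for the others), the 9.6 rule gives 1.40 or 1.25 and the absence rule 1.48 or 1.46. In a simpler run, 25% or 50% of all 180 patients were early events, giving 1.35 or 1.22. Letting a quarter of them worsen within 24 hours moved this to 1.39 or 1.29. Control medians of 7 or 14 days gave 1.37 or 1.35 at 25%, and 1.25 or 1.21 at 50%.

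**The case against.** **A tiered rule may be meant.** Absence could apply to patients who start mild, and mild or absent to those who start worse, since the synopsis admits mild to moderate symptoms. This is plausible but written nowhere, and 9.6 makes no split by baseline severity.

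**The SAP may settle it.** It can, if it fixes one definition before unblinding. Deferral does not remove a conflict between two rules already stated in the protocol, but it does lower the urgency.

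**Both endpoints are legitimate.** Time to absence and time to mild or absent are different quantities, and nothing in the documents ranks one above the other. This stands. The illustration sets 1.5 for one rule and shows what entry-level events do under the other. It does not measure how the two definitions differ in patients who start worse than mild.

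**A reader might infer that asymptomatic patients become early events because 9.4 puts every efficacy analysis in ITT.** That is the less plausible reading. Cessation presupposes a symptom, endpoint 5 is worded for patients with mild symptoms, and endpoint 6 covers the asymptomatic. Analysing an endpoint by assigned arm in the patients for whom it is defined need not conflict with ITT. What remains is that the analysis set should be named.

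**A reader might also infer that every symptomatic patient meets the 9.6 rule at entry.** The documents do not support this, because entry as mild disease is not a grade per symptom.

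**Conclusion.** The point holds. Endpoint 5 and Section 9.6 give different rules for the same event, nothing reconciles them, and 9.6 taken literally makes patients whose symptoms are all mild at baseline events at about the first diary unless they worsen. The analysis set is not stated, and the two diary lists clearly differ on runny nose and rash.

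The size is unknown. Under the assumptions above, the 9.6 rule gives a hazard ratio of about 1.40 or 1.24 where the absence rule gives 1.5, and the medians shorten in both arms. A general statement that the 9.6 rule pulls the hazard ratio toward 1 would go too far: the result depends on the assumed share and on equal event times under both rules for patients worse than mild.

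This is a secondary endpoint with no stated power. The primary analysis is unaffected. It should be corrected before unblinding.

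**What to change.** Before unblinding:

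1. **Definition.** In 9.6, use the endpoint 5 rule: absence of all listed symptoms for at least 24 hours. State how 24 hours is determined from a daily diary.
2. **Analysis set.** Analyse by assigned arm all randomised patients with at least one symptom on the Day 1 baseline survey, and name this set for the endpoint in 9.4.
3. **Asymptomatic patients.** Analyse patients with no baseline symptom under endpoint 6, and describe the duration of any later-onset symptoms separately.
4. **Diary.** Use one list in the synopsis and 8.1. The 8.1 list covers every entry symptom; remove its duplicate abdominal pain item and check its blank item. State the temperature value that counts as absent.
5. **If mild or absent is kept**, label it supplementary and restrict it to patients with at least one symptom worse than mild at baseline.

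The cost is wording in 9.4, 9.6, the diary lists and the SAP. The baseline survey and daily diary are already planned; the supplementary analysis also needs a grade per symptom in the survey. The downsides are a smaller set than ITT (162 rather than 180 in the illustration) and longer event times than under mild or absent.
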